The exact location of the electronic data is S:\Research\[name]\H-36912

Database location will be on a VA server

Will there be anyone besides the PI, the study staff, the IRB and the sponsor, who will have access to identifiable research data?

Yes, identify the classes of the persons:

People who ensure quality from the institutions where the research is being done, federal and other regulatory agencies will have access to all of the research data such as Food and Drug Administration (FDA) and Data

Monitoring Committee (DMC). The purpose of collecting information covered under 38 U.S.C. 7332 is to conduct scientific research and no personnel involved in this study will identify, directly or indirectly, any individual patient or subject in any report of such research.

Please describe the methods of transmission of any research data (including PHI, sensitive, and non-sensitive data) to sponsors and/or collaborators.

Data will not leave the MEDVA.

Will you obtain a Certificate of Confidentiality for this study?

No

Please further discuss any potential confidentiality issues related to this study.

Research records, including identifiers will be destroyed 6 years after cutoff (at the end of the fiscal year) after completion of the research project, but may be retained longer if required by other federal regulations or sponsor archive requirement.

Section L: Cost/Payment

Delineate clinical procedures from research procedures. Will subject's insurance (or subject) be responsible for research related costs? If so state for which items subject's insurance (or subject) will be responsible (surgery, device, drugs, etc). If appropriate, discuss the availability of financial counseling.

Subjects are not responsible for any costs related to participation in the research.

If subjects will be paid (money, gift certificates, coupons, etc.) to participate in this research project, please note the total dollar amount (or dollar value amount) and distribution plan (one payment, pro-rated payment, paid upon completion, etc) of the payment.

Dollar Amount:

60

Distribution Plan:

Subjects will be paid 20\$ at baseline, 3 and 6 months. Total payment for completing the study will be 60\$ per patient.

Section M: Genetics

How would you classify your genetic study?

DNA diagnostic study

Discuss the potential for psychological, social, and/or physical harm subsequent to participation in this research. Please discuss, considering the following areas: risks to privacy, confidentiality, insurability, employability, immigration status, paternity status, educational opportunities, or social stigma.

There is an associated genetic risk if the genetic information is leaked which may affect a subjects insurability.

However, all of the patients are veterans getting medical care at the Michael DeBakey VA Medical Center whose benefits will not terminate with any breach of genetic information. In addition, since the type of genetic variations that this study is investigating are common genetic variations in the population, we foresee no consequences on the patients employability, immigration status, educational opportunities or social stigma and not useful in establishing paternity.

Will subjects be offered any type of genetic education or counseling, and if so, who will provide the education or counseling and under what conditions will it be provided? If there is the possibility that a family's pedigree will be presented or published, please describe how you will protect family member's confidentiality?

No, subjects will not be offered any type of genetic education or counseling. There is not the possibility that a family's pedigree will be presented or published. The results of the genetic testing will not be given to the subjects. As the patients blood sample will not be linked to the patients identity, we plan to match the subjects identity with their DNA results with a study code assigned to each subjects DNA results which can only be interpreted with a special decrypting file.

Section N: Sample Collection SAMPLE: Other: blood

What is the purpose of the sample collection?

Blood samples will be collected for 1) medical screening to determine eligibility for the study (see inclusion/exclusion criteria, 2) to monitor blood levels of testosterone, estradiol, LH, FSH and side effects on blood count and PSA, 3) overall safety monitoring while in the study

For blood draws, specify the amount drawn, in teaspoons, at each visit and across the course of the subjects entire participation time.

A total of 4 tablespoons of blood at baseline and 6 months, and 3 tablespoons at 2 weeks and at 3 months. Total amount of blood collected for participating in the study 14 tablespoons.

Is there the possibility that cell lines will be developed with this sample? No

Sample will be obtained from:

Clinical Labs, Research Labs

Will the sample be stripped of identifiers?

No

If sample will be released outside the hospital:

Will sample be released to anyone not listed as an investigator on the protocol? Will the information be identifiable, coded or de-identified?

Yes, to BCM collaborators. All samples will be coded using random numbers not linked to SSN.

Will sample material be sold or transferred to any third parties? Will the information be de-identified?

No.

If sample will be banked for future use:

Where will the sample be banked and for how long?

At the Michael DeBakey VA Medical Center for 10 years

Does the banking institution have an approved policy for the distribution of samples?

Yes.

If the entire sample will NOT be used during the course of this research study:

Will the remaining tissue be discarded? If not what will be done with the remaining sample after study completion and how long will the sample be kept?

We will keep the samples for 10 years after study completion after which they will be discarded.

Will samples be made available to the research subject (or his/her medical doctor) for other testing?

No

If a subject withdraws from the study:

Will subject have the option to get the remaining portion of their sample back?

No

Will samples be destroyed? If not, will they be kept anonymously? What will happen to the sample if the subject revokes authorization?

If the patient withdraws from the study, samples will not be destroyed and will be stored anonymously. If the subject revokes authorization, the samples will be destroyed or discarded.

Will data obtained from their sample be deleted? What will happen to the sample if the subject revokes authorization?

For those who withdraw from the study, we will use the data generated from the samples. However, for subjects who revoked authorization, their data will be deleted and samples destroyed or discarded.

Will study data or test results be recorded in the subject's medical records?

Yes

Will results of specific tests and/or results of the overall study be revealed to the research subject and or his/her doctor?

Standard test results that are done at VA lab and have clinical use are reported in CPRS, or Computerized Patient Record System, and thus they are automatically included in the subjects medical records (i.e. in CPRS, which is accessible to the vets primary provider). Any abnormal findings will be shared with the subject's primary care physicians for further evaluation and appropriate treatment through the CPRS which are shared with their VA primary care physicians. Depending on the urgency of the abnormal findings, the PI may directly contact the primary care provider by phone to discuss the abnormal findings

Please identify all third parties, including the subject's physician, to receive the test results.

Participants treating physicians.

SAMPLE: Blood

What is the purpose of the sample collection?

1) DNA collection to investigate the impact of the genetic profile on the response to anastrozole and/or weight loss intervention.

For blood draws, specify the amount drawn, in teaspoons, at each visit and across the course of the subjects entire participation time.

A total of 1 tablespoons of blood at baseline, 3 months and 6 months. Total amount of blood collected for genetic testing for participating in the study is 3 tablespoons.

Is there the possibility that cell lines will be developed with this sample? No

Sample will be obtained from:

Research Labs

Will the sample be stripped of identifiers?

No

If sample will be released outside the hospital:

Will sample be released to anyone not listed as an investigator on the protocol? Will the information be identifiable, coded or de-identified?

Yes, to BCM collaborators. All samples will be coded using random numbers not linked to SSN.

Will sample material be sold or transferred to any third parties? Will the information be de-identified?

No

If sample will be banked for future use:

Where will the sample be banked and for how long?

At the Michael DeBaKey VA Medical Center for 10 years

Does the banking institution have an approved policy for the distribution of samples?

Yes

If the entire sample will NOT be used during the course of this research study:

Will the remaining tissue be discarded? If not what will be done with the remaining sample after study completion and how long will the sample be kept?

We will keep the samples for 10 years after study completion after which they will be discarded.

Will samples be made available to the research subject (or his/her medical doctor) for other testing?

No

If a subject withdraws from the study:

Will subject have the option to get the remaining portion of their sample back?

No

Will samples be destroyed? If not, will they be kept anonymously? What will happen to the sample if the subject revokes authorization?

If the patient withdraws from the study, samples will not be destroyed and will be stored anonymously. If the subject revokes authorization, the samples will be destroyed or discarded.

Will data obtained from their sample be deleted? What will happen to the sample if the subject revokes authorization?

For those who withdraw from the study, we will use the data generated from the samples. However, for subjects who revoked authorization, their data will be deleted and samples destroyed or discarded.

Will study data or test results be recorded in the subject's medical records?

Yes

Will results of specific tests and/or results of the overall study be revealed to the research subject and or his/her doctor?

Standard test results that are done at VA lab and have clinical use are reported in CPRS, or Computerized Patient Record System, and thus they are automatically included in the subjects medical records (i.e. in CPRS, which is accessible to the vets primary provider). Any abnormal findings will be shared with the subject's primary care physicians for further evaluation and appropriate treatment through the CPRS which are shared with their VA primary care physicians. Depending on the urgency of the abnormal findings, the PI may directly contact the primary care provider by phone to discuss the abnormal findings.

Please identify all third parties, including the subject's physician, to receive the test results.

Participants treating physicians.

Section O: Drug Studies

Does the research involve the use of ANY drug* or biologic? (*A drug is defined as any substance that is used to elicit a pharmacologic or physiologic response whether it is for treatment or diagnostic purposes)

Yes

Does the research involve the use of ANY gene transfer agent for human gene transfer research?

No

O1. Current Drugs [Drug : Arimidex 1 mg \(anastrozole 1 mg tablet for oral use\)](#)

Is this study placebo-controlled?

Yes

If yes, be sure that you justify the use of the placebo for this research in the space below.

The placebo controlled trial is required to evaluate which is the best approach for the treatment of hypogonadotropic hypogonadism in severely obese men: life style intervention induced weight loss alone (placebo group) or life style intervention induced weight loss combined with anastrozole therapy (active group).

IND # 126696

Will the research involve a radioactive drug that is not approved by the FDA?

No

Section P: Device Studies

Does this research study involve the use of ANY device?

No

Section Q. Consent Form(s)

None

Section R: Advertisements Mode of Advertising: Bulletin Board

Exact language of Advertisement:

Below is the exact language of the advertisement for the study: This study is looking at the effect of weight loss alone or in combination with anastrozole, a medication which may increase testosterone levels, on muscle strength and symptoms related to low circulating testosterone. VOLUNTEERS MUST: - Be a male veteran - Be age 35-65 - Be obese - Not have prostate cancer - Not have a history of bariatric surgery - Not be on testosterone DURATION and LOCATION- Participation in the study will be 6 months. The study is conducted by Baylor College of Medicine and the Michael E. DeBakey VA Medical Center. The study will take place at the Michael E. DeBakey, Houston VA. INTERVENTION- Participants will take either the active drug (anastrozole) or placebo in addition to participation in a weight loss program (diet+exercise) TEST/PROCEDURES - Include phone screening, orientation session, medical examination, strength testing, bone mineral density and body composition testing and simple blood testing. COMPENSATION- Volunteers may receive up to \$60.00. PI: [name], M.D. [name] or [name]

Mode of Advertising: Other: Flyers

Exact language of Advertisement:

Below is the exact language of the advertisement for the study: Testosterone study

This study is looking at the effect of weight loss alone or in combination with anastrozole, a medication which may increase testosterone levels, on muscle strength and symptoms related to low circulating testosterone.

VOLUNTEERS MUST: - Be a male veteran - Be age 35-65 - Be obese (BMI >35) - Not have prostate cancer - Not have a history of bariatric surgery - Not be on testosterone

DURATION - Participation in the study will be 6 months. The study is conducted by Baylor College of Medicine and the Michael E. DeBakey VA Medical Center. The study will take place at the Michael E. DeBakey, Houston VA.

INTERVENTION- Participants will take either the active drug (anastrozole) or placebo in addition to participation in a weight loss program (diet+exercise)

TEST/PROCEDURES - Include phone screening, orientation session, medical examination, strength testing, bone mineral density and body composition testing and simple blood testing.

COMPENSATION- Volunteers may receive up to \$60.00.

PI: [name], M.D. [name] or [name]

Mode of Advertising: BCM Clinical Trials Website

Exact language of Advertisement:

Below is the exact language of the advertisement for the study: This study is looking at the effect of weight loss alone or in combination with anastrozole, a medication which may increase testosterone levels, on muscle strength and symptoms related to low circulating testosterone. VOLUNTEERS MUST: - Be a male veteran - Be age 35-65 - Be obese - Not have prostate cancer - Not have a history of bariatric surgery - Not be on testosterone DURATION and LOCATION- Participation in the study will be 6 months. The study is conducted by Baylor College of Medicine and the Michael E. DeBakey VA Medical Center. The study will take place at the Michael E. DeBakey, Houston VA. INTERVENTION- Participants will take either the active drug (anastrozole) or placebo in addition to participation in a weight loss program (diet+exercise) TEST/PROCEDURES - Include phone screening, orientation session, medical examination, strength testing, bone mineral density and body composition testing and simple blood testing. COMPENSATION- Volunteers may receive up to \$60.00. PI: [name], M.D. [name] or [name]

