
Section D: Purpose and Objectives

OBJECTIVES: 1. To evaluate the effect of AIs in combination with weight loss compared to weight loss alone on the changes in muscle strength, and symptoms of hypogonadism in massively obese men with hypogonadotropic hypogonadism 2. To evaluate the effect of AIs in combination with weight loss compared to weight loss alone on the changes in body composition and visceral adipose tissue in massively obese men with hypogonadotropic hypogonadism. 3. To evaluate the effect of AIs in combination with weight loss compared to weight loss alone on bone mineral density and bone quality in massively obese men with hypogonadotropic hypogonadism. We hypothesize that in severely obese men with HH, the combination of AI therapy and weight loss intervention would be an effective alternative treatment strategy in improving HH related signs and symptoms without the adverse effect on bone metabolism.

Section E: Protocol Risks/Subjects E1. Risk Category

Category 2: Research involving greater than minimal risk, but presenting the prospect of direct benefit to the individual subjects.

E2. Subjects

Gender:

Male

Age:

Adult (18-64 yrs), Geriatric (65+ yrs)

Ethnicity:

All Ethnicities

Primary Language:

English

Groups to be recruited will include:

Patients

Which if any of the following vulnerable populations will be recruited as subjects?

Vulnerable populations require special protections. How will you obtain informed consent, protect subject confidentiality, and prevent undue coercion?

E3. Pregnant woman/fetus

Will pregnant women and/or fetuses (as described in 45 CFR 46 Subpart B) be enrolled in the research?

No

E4. Neonates

Will neonates of uncertain viability or nonviable neonates (as described in 45 CFR 46 Subpart B) be enrolled in the research?

No

E5. Children

Will children be enrolled in the research?

No

Section F: Design/Procedure F1. Design

Select one category that most adequately describes your research:

c) Pilot

Discuss the research design including but not limited to such issues as: probability of group assignment, potential for subject to be randomized to placebo group, use of control subjects, etc.

See attachment entitled " F1 Design IRB 7.29"

Inclusion Criteria:

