1. Medical, social and medication history, and physical examination, body weight and height will be repeated at 3 and 6 months. DRE will be repeated at 6 months. An additional physical examination (except for digital rectal exam) will be done after 2 weeks from the start of the intervention for safety monitoring. 2. The ADAM quantitative questionnaire, IIEF questionnaire, Stanford physical activity 7 days recall questionnaire, SF-36 questionnaire and the IWQOL will be administered at baseline, 3 and 6 months. 3. Muscle strength by Biodex will be assessed at baseline, 3 and 6 months (not standard of care). 4. Participants will be given instructions for keeping 7-day food intake records and provided with recording forms to estimate energy intake and nutrient composition. The food intake records will be analyzed using the Nutritionist IV computer program (N2 Computing, San Bruno, CA). The Stanford 7-Day Physical Activity Questionnaire will be used to quantify the time spent in different categories of activity during the previous 7 day period. Participants will also be asked to wear accelerometers for the whole intervention and to report daily data concerning the instrument usage. 5. Blood will be collected at 2 weeks a for testosterone, estradiol, LH and FSH, AST, ALT,ALP and bilirubin and at 3 and 6 months for repeat PSA, total testosterone, CBC, CMP, lipid panel, HbA1C, ALP, AST, ALT and bilirubin, markers of bone turnover, estradiol, SHBG, LH, FSH, 25-hydroxy vitamin D and PTH (all test are standard of care except for estradiol and SHBG). 6. Bone mineral density will be measured using DXA, QCT, and HR-pQCT at baseline and 6 months. TBS will be calculated at baseline and 6 months, whereas body composition and visceral adipose tissue volume will be measured at baseline, 3 and 6 months, both will be assessed using DXA. 7. At baseline, 3 and 6 month, blood will be drawn for extraction of DNA, which is part of the cell and os responsible for providing hereditary characteristics. The purpose of analyzing DNA is to determine whether hereditary characteristics are associated with obesity induced HHG and whether the response to weight loss and AI administration is affected by them

Section G: Sample Size/Data AnalysisG1. Sample Size

How many subjects (or specimens, or charts) will be used in this study?

Local: 23 Worldwide: 30

Please indicate why you chose the sample size proposed:

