This is a pilot study with the primary objective of gathering preliminary feasibility and effectiveness data for the development of a bigger study. We plan to enroll 30 subjects for this study. In prior studies of patients with HH using sample sizes of 20-40, a significant increase in T levels was observed for those on AIs compared to those without AIs. In our proposed study, we anticipate a greater increase in T in our patient's randomized to AI over and above the increase resulting from weight loss alone by the same magnitude of increase in above studies which compared the effect of AI alone to those not on AI. Thus, a sample of 30 was chosen for this pilot study. Although the above studies did not include changes in hypogonadal symptoms as outcomes, we anticipate greater improvement in symptoms of hypogonadism among patients on AIs plus weight loss. It is highly likely that we may not be able to find a statistically significant difference between the AIs plus weight loss vs. weight loss alone group in our primary outcomes given this limited sample size, but our results would still provide important information for a bigger study if a trend is observed.

G2. Data Analysis

Provide a description of your plan for data analysis. State the types of comparisons you plan (e.g. comparison of means, comparison of proportions, regressions, analysis of variance). Which is the PRIMARY comparison/analysis? How will the analyses proposed relate to the primary purposes of your study?

Baseline characteristics between groups will be compared using independent t-test or Fisher's exact test. Percent changes in outcomes at 3 and 6-month time points will be compared between the 2 groups using repeated measures analysis of covariance adjusting for covariates such as age, ethnicity and medication use as appropriate. A p value of <0.05 will be considered significant. Simple correlations will be analyzed using Pearson correlation coefficient.

Given the limited sample size, it is possible that we may not find a significant difference in outcomes between the anastrozole+weight loss vs. weight loss alone but the information generated from this pilot study will still be useful if a trend is observed for future proposals or plan for additional recruitment to enhance the sample size.

Section H: Potential Risks/Discomforts H1. Potential Risks/Discomforts

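### Section G2's p<0.05 comparison of percent change cannot support the no-bone-harm part of the hypothesis in about 30 men; report baseline-adjusted bone differences with 95% CIs

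*Combined protocol and SAP*

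**What the plan says.** Objective 3 in Section D is "To evaluate the effect of AIs in combination with weight loss compared to weight loss alone on bone mineral density and bone quality". The hypothesis that closes the section goes further: it expects that the combination "would be an effective alternative treatment strategy in improving HH related signs and symptoms without the adverse effect on bone metabolism", and bone is the only harm it names.

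Section G2 gives one follow-up analysis for all outcomes: "Percent changes in outcomes at 3 and 6-month time points will be compared between the 2 groups", by repeated-measures analysis of covariance, "adjusting for covariates such as age, ethnicity and medication use as appropriate". The decision rule is "A p value of <0.05 will be considered significant". The rest of G2 covers baseline group comparisons and Pearson correlations. It mentions no confidence interval, does not treat bone separately, and does not name the baseline value of the outcome as a covariate.

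The schedule is in Section F2, follow-up testing. Item 6 says "Bone mineral density will be measured using DXA, QCT, and HR-pQCT at baseline and 6 months", and the trabecular bone score (TBS) follows the same two visits. Bone turnover markers (item 5) are repeated at both 3 and 6 months.

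Section G1 gives the pilot's purpose as "gathering preliminary feasibility and effectiveness data for the development of a bigger study". It concedes that significance on the primary outcomes is unlikely, and adds that "our results would still provide important information for a bigger study if a trend is observed". The design attachment (F1) and the safety-monitoring attachment (H2) are not in the supplied text.

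**The concern.** A hypothesis that something is absent is paired with a test that can only detect that it is present. If the bone comparison gives p≥0.05, G2 offers nothing else to report, and a small trial can easily give that result when there is a real loss. The G1 and G2 remarks about a useful trend are general; they do not say how a null bone result is to be read.

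The protocol's own use of earlier evidence shows how this can go wrong. Section C says that the design of one earlier six-month study prevented a firm conclusion. Section H1 then cites the same study as having shown no bone loss.

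The larger study that this pilot is meant to inform needs to know how much bone loss is still compatible with the data. A difference with its interval answers that; a p value alone does not.

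**Working it through.** **The plan's own figure.** The sample of 30 cannot be reproduced. G1 bases it on earlier studies of testosterone with 20 to 40 patients and gives no effect size, SD, power or acceptable bone loss. The check therefore asks what 30 men can show about bone, in SD units.

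**Inputs.** N = 30 (G1) and alpha = 0.05 (G2). Assumed, because the supplied text does not say: equal allocation (15/15), a two-sided test, complete bone data, a normal outcome and no covariates. SD means the SD of whichever outcome is analysed.

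**Step 1: width of the interval.**
Half-width = t(0.975, n1+n2−2) × √(1/n1 + 1/n2).
15/15: 2.048 × √(2/15) = 2.048 × 0.365 = 0.748 SD.
Even if the observed difference were exactly zero, an extra loss of about 0.75 SD would still lie at the edge of the interval.

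**Step 2: how often a real loss is missed.**
The test statistic follows a noncentral t with 28 degrees of freedom and noncentrality d / √(2/15), where d is the true extra loss in SD.

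| True extra loss | P(p≥0.05), 15/15 |
|---|---|
| 0.5 SD | 73.8% |
| 0.75 SD | 49.1% |
| 1.0 SD | 24.7% |

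A simulation of 200,000 trials also gives 73.8% at 0.5 SD. The loss detected with 80% power is 1.06 SD, so large losses would usually be found and moderate ones often would not.

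**Step 3: sensitivity to numbers.** G1 gives 23 as the local count; it serves here only as a low end. With 12/11, the half-width is 2.080 × √(1/12 + 1/11) = 0.868 SD, and the miss rates are 79.2%, 59.7% and 37.3%.

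**Step 4: what baseline adjustment changes.** Let r be the correlation between the baseline and 6-month values, which the documents do not give. In units of the SD of the 6-month value, the half-width is t × √(2/15) × √(2(1−r)) for a simple change score (28 df) and t × √(2/15) × √(1−r²) for ANCOVA (27 df).

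| r | Change score | ANCOVA |
|---|---|---|
| 0.5 | 0.75 | 0.65 |
| 0.7 | 0.58 | 0.54 |
| 0.9 | 0.34 | 0.33 |

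Percent change, 100 × (6-month − baseline)/baseline, uses baseline as a divisor. It does not estimate how the 6-month value depends on baseline, so it does not do the same job as a covariate.

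**Step 5: visits against the model.** Bone imaging and TBS have one post-baseline value, so G2's 3-month comparison has no data for them and the model reduces to a 6-month comparison. The turnover markers have two post-baseline values and fit the repeated-measures model.

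**The case against.** The strongest reply is that the plan never commits the error. Section D states an expectation and no decision rule, objective 3 only evaluates, and both G1 and G2 warn that significance may not be reached. This stands. A reader might infer that the trial will declare bone safe if p≥0.05, but no supplied text says so.

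Second, a reader might infer that G2 rules out baseline adjustment. It does not: the covariate list is open. Where r is high, adjustment also gains little precision (0.34 against 0.33 SD at r = 0.9). Naming baseline is therefore a recommendation and not the repair of an exclusion. It still removes an ambiguity and allows for chance imbalance.

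Third, the visit mismatch might be read as making the bone analysis unworkable. It is mostly a drafting matter, since one follow-up value leaves only the 6-month comparison.

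Fourth, G2 is silent on intervals for every outcome, and the planned model could produce them without any design change. That is true. The omission matters most for bone, because bone is where the hypothesis asserts an absence.

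Finally, the SD figures come from an unadjusted t test, which is neither G2's model nor the one proposed here, and the documents do not say what loss would matter. The figures illustrate the limit and do not measure a consequence.

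**Conclusion.** The point holds, and it is minor. As supplied, G2 cannot support the no-harm half of the Section D hypothesis, because p≥0.05 in about 30 men is compatible with a moderate bone loss. The half-width of about 0.75 SD and the miss rate of about 74% at 0.5 SD rest on 15/15, complete data, a two-sided test and no adjustment. Baseline adjustment would narrow the interval by an amount that depends on r.

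It would go too far to call the sample size wrong or to demand a non-inferiority margin. This is a declared pilot with acknowledged low power, and estimation is the proportionate aim. The conclusion is limited to the supplied text; the design and safety-monitoring attachments may add rules on bone.

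**What to change.** In Section G2, add:

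- Bone imaging outcomes (bone density by DXA, QCT and HR-pQCT, and TBS) are analysed by ANCOVA of the 6-month value, with the baseline value as covariate and any other prespecified covariates kept.
- Bone turnover markers are analysed at 3 and 6 months by the repeated-measures model, with the baseline value as covariate.
- Each anastrozole-minus-placebo difference is reported with its 95% CI as the main bone result.
- p≥0.05 will not be taken as evidence of no bone effect.

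In Section D, say that the effect on bone will be estimated.

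The cost is a few sentences. Baseline values are already collected, so no scans or patients are added. The covariate uses one degree of freedom, and the bone conclusion will probably have to be stated as inconclusive. If the unsupplied attachments contain bone rules, the new text should be checked against them.

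### Do 23 local and 30 worldwide subjects in a study described at one site mean that the planned sample of 30 is wrong?

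*Combined protocol and SAP*

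**What the plan says.** Section G1 (Sample Size) answers the form's question on the number of subjects with "Local: 23 Worldwide: 30". The rationale beneath it says "We plan to enroll 30 subjects for this study" and ends "Thus, a sample of 30 was chosen for this pilot study". The basis is precedent: "In prior studies of patients with HH using sample sizes of 20-40, a significant increase in T levels was observed". G1 gives no effect size, standard deviation, power target or dropout rate, and it says of the primary outcomes: "It is highly likely that we may not be able to find a statistically significant difference".

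Section G2 (Data Analysis) plans a repeated measures analysis of covariance on percent changes at 3 and 6 months. Age, ethnicity and medication use are given as examples of covariates, to be used as appropriate. On the test level it says only "A p value of <0.05 will be considered significant".

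On location, Section M (Genetics) says "all of the patients are veterans getting medical care at the Michael DeBakey VA Medical Center", and the advertisements in Section R say "The study will take place at the Michael E. DeBakey, Houston VA". Section J2 describes recruitment as mainly from three clinics at that centre. Section H3 replies in the negative, or as not applicable, to two questions: whether the Baylor investigator is sponsor-investigator for multi-site research, and whether Baylor is its coordinating centre.

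**The concern.** A local count below the worldwide count normally means that another site enrols the difference. No other site is named here, and Section M, read literally, puts every patient at Houston. So either the trial has 23 men and the rationale rests on too large a number, or 7 men come from a place the document does not describe and the analysis model does not mention.

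This could matter because the total is the only planning number in the protocol, and the pilot is meant to inform a larger study. With 23 men the estimates would be less precise than a reader expecting 30 would assume. With two sites, differences in dynamometer, DXA scanner or lifestyle programme could add variation to the comparison.

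A related point is that the rationale rests on change in testosterone, whereas the three objectives in Section D concern strength, symptoms, body composition and bone.

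**Working it through.** **1. Can the 30 be reproduced?** No. G1 gives no statistical inputs, only precedent studies of 20–40 subjects. There is therefore no calculation for 23 to contradict, and 23 lies in the same range.

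**2. Do 23 and 30 conflict?** As numbers, no. Local is a subset of worldwide, 30 − 23 = 7, and 7/30 = 23.3%. The rationale in G1 also uses 30 as the total. The tension is between the form entry in G1 and the single-centre statements in Sections M and R.

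**3. Could 23 be the number left after dropout?** 23/(1 − 0.23) = 29.9, so a loss of about 23% would connect the two figures. No dropout rate is stated and the form labels the figures local and worldwide, so this reading has no support.

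**4. What would be lost if only 23 were enrolled?** Assumptions: two-sided α = 0.05 (G2 gives the level but not the sidedness), equal allocation (the ratio is not in the available text), and an unadjusted two-sample t-test as a stand-in for the planned model. Splits are 15/15 and 12/11.

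- Standard error in SD units, √(1/n₁ + 1/n₂): √(1/15 + 1/15) = 0.365; √(1/12 + 1/11) = 0.417.
- Detectable difference at 80% power, normal approximation, (1.960 + 0.842) × SE: 1.02 SD and 1.17 SD. Noncentral t: 1.06 SD and 1.23 SD.
- 95% interval half-width, t(0.975, n₁ + n₂ − 2) × SE: 2.048 × 0.365 = 0.75 SD; 2.080 × 0.417 = 0.87 SD. The ratio is 1.16.

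Power from the noncentral t, over a range of assumed true differences:

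| True difference (SD) | 30 men | 23 men |
|---|---|---|
| 0.5 | 26% | 21% |
| 0.8 | 56% | 45% |
| 1.0 | 75% | 63% |
| 1.06 | 80% | 68% |
| 1.2 | 89% | 78% |

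The 1.06 SD row is obtained by solving back from 30 men. It is not a target that the plan sets. On either count, only a difference of more than one SD is detected with 80% power, which is in line with what G1 concedes.

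**5. What if a second site contributed?** The G2 covariates are examples, not a closed list, so site can be added. The outcomes are percent changes. If a device reads high or low by a constant factor k, and each man is measured on the same device throughout, (k·y₁ − k·y₀)/(k·y₀) = (y₁ − y₀)/y₀, so the factor cancels. Additive offsets and differences between lifestyle programmes would not cancel, and a site term is the usual way to handle them.

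**The case for a change.** The strongest case for a change is that Section M says all patients are cared for at Houston, which leaves no room for 7 men from elsewhere. On that view one of the two statements must be edited whichever is right, and a pilot whose product is precision and feasibility should be clear about its own total. The figures above are also not trivial: a 16% wider interval and a 12-point loss of power at 1.06 SD.

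Part of this stands. The source of the 7 men is unexplained, and G1 and Section M do not fit together if both are read literally as covering the whole trial. The observation that the rationale uses testosterone rather than strength or symptoms is also accurate.

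The rest does not carry through. Section M and the advertisements belong to one institution's ethics form and may describe local conduct only. H3 asks about the investigator's and institution's roles, and its answers do not say whether another site exists. The design itself is deferred to an attachment named in Section F1 that is not part of the available text, so an explanation there cannot be ruled out. The testosterone point is separate from 23 versus 30, and no power is claimed for strength or symptoms that it would undermine.

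**Conclusion.** The concern does not hold as a fault in the plan. The documents consistently give 30 as the total, with 23 of them local. What is missing is a line on where the other 7 come from, which is a gap in description.

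Restating the total as 23 would contradict the plan's own figure on no better evidence. Stating a detectable difference would record information without altering what is done. A site term would matter only if a second site exists, which is not established, and the G2 wording already permits one. An analyst would analyse the men randomised, report the actual number and intervals, and add site if more than one contributed. Following the plan as written would not give a wrong result.

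The most that is at stake is the step from about 1.06 to 1.23 SD in detectable difference, assuming equal allocation, a two-sided 5% level and a simple two-group comparison. The plan makes no precision claim that this step would break.
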